The least square mean (LS Mean) of each treatment group (placebo and SPN-538) along with the corresponding standard error, p-values, difference in the LS Mean between SPN-538 and placebo (SPN-538 minus placebo), and 95% CIs will be computed at each visit.

Sensitivity analyses will be performed based on MI, assuming that missing data are MNAR.

Secondary Endpoint Analyses:

Secondary endpoints will be analyzed based on the FAS using appropriate statistical models.

Safety Analyses:

Safety analyses will be performed by treatment group using the Safety Analysis Set. The incidence rate, severity, and relationship to the SM for all AEs will be summarized by treatment group, system organ class (SOC), and preferred term (PT).

Descriptive statistics will be presented for demographics, data from the clinical laboratory test results, vital signs, weight, ECGs, physical, neurological and eye examinations, suicidal ideation, and cognitive assessment.

Inclusion Criteria:

1. Healthy male or female subjects, 6 to 11 years of age (inclusive) at Screening.
2. History of migraine with or without aura conforming to the International Headache Society (IHS) criteria for pediatric subjects (International Classification of Headache Disorders, 3rd edition [ICHD-3]) for at least 6 months prior to Screening.

3. Subjects who experience 3-12 migraine episodes and no more than 14 headache days (migraine and non-migraine) per month during the 3 months prior to Screening and during the 28-day Prospective Baseline Period (based on the Headache Diary).
4. At Screening, a PedMIDAS Disability score of ≥ 20 (indicating at least mild disruption of daily activities) and ≤ 139 (indicating severe disability that may require more comprehensive therapy).
5. Weight of at least 20 kg and no more than 60 kg (inclusive) at the Randomization visit (Visit 3).
6. Considered medically healthy by the Investigator via assessment of physical, neurological and eye examinations, medical history, clinical laboratory tests, vital signs, and ECGs.
7. Able and willing to swallow capsules whole and intact without sprinkling on food, crushing, chewing, cutting, or dissolving before swallowing.
8. Caregiver must be able to read and comprehend written instructions and be willing to supervise the completion of all headache records and questionnaires by the subject as required in the protocol.

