3 INVESTIGATIONAL STUDY PLAN

3.1 Overall Study Design and Plan

This is a multicenter, randomized, double-blind, placebo-controlled, 2-arm, parallel group Phase 4 study in children 6 to 11 years of age to evaluate the efficacy and safety of SPN-538 for the prevention of migraine. SPN-538 (or matching placebo) will be administered as a single oral dose QD, starting at 25 mg/day and increasing every 2 weeks in 25 mg increments to a target dose of 2 to 3 mg/kg/day or the maximum tolerated dose (MTD), whichever is less. The total study duration is a maximum of 34 weeks, including a Screening Period and a Prospective Baseline Period of up to 8 weeks; a Treatment Phase of 20 weeks (8 weeks titration followed by 12 weeks of maintenance dosing); a Dose Tapering Period of 1 to 3 weeks; and a Safety Follow up period of 1 to 3 weeks. Approximately 35 sites in the United States (US) are planned. The study schematic is shown in [Figure 1](#) and described below.

Pre-treatment Phase

Screening Period (Visit 1, up to 8 weeks before Visit 3)

At Visit 1, informed consent and informed assent (if applicable) will be obtained. Initial screening evaluation includes headache history, medical, family and psychiatric histories, ECG and vital sign assessments, physical and neurological examinations,

concomitant medications, headache disability, and laboratory tests including hematology, chemistry, urinalysis, drug screen, and serum pregnancy test (females of childbearing potential [FOCPs] only). Suicidality will be evaluated using the C-SSRS, Children's version. A visual neurological examination will also be required prior to Visit 2 ([Section 6.8.5](#)).

Subjects treated with the following prophylactic medications should discontinue the treatment 14 days prior to the Prospective Baseline Period: antipsychotics, antimanics, barbiturates, benzodiazepines amitriptyline, lithium, valproic acid, tricyclic antidepressants, AEDs, calcium channel blockers, sedatives, serotonin selective reuptake inhibitors (SSRIs), non-selective reuptake inhibitor (NSRIs), calcitonin gene-related peptide (CGRP) receptor antagonists, cannabidiol (CBD) oil, herbal preparations/supplements such as feverfew or St John's wort and/or any medications that could impair or decrease thinking and concentration. It is recommended to taper off antipsychotics, barbiturates, benzodiazepine, tricyclic antidepressants, lithium, amitriptyline, valproic acid, SSRIs and NSRIs as applicable ([Appendix 10.10](#)).

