and tolerability during this period. Additional dose titration related to body weight changes will be reviewed and approved by the Medical Monitor and the Sponsor on a case by case basis. The number, severity, and symptoms of all headaches, as well as the type and dose of rescue medication and SM compliance will be recorded daily in the Headache Diary. During the Maintenance Period, clinic visits will be scheduled every 4 weeks. During each clinic visit, a 4-week supply of SM will be provided, and SM compliance and the Headache Diary will be reviewed. Safety evaluations, including vital signs, concomitant medications, cognitive assessment, C-SSRS, clinical laboratory tests (only at Visit 8), urine pregnancy test (FOCP only), urine drug screen, physical and neurological evaluations will also be performed. [REDACTED]

[REDACTED]

During Visit 6, the eye exam will be performed, and another refresher placebo training will be administered.

Telephone contacts will occur at the intervening 2-week periods [Days 71, 99 and 127 (± 2 days)] between clinic visits for safety assessment and to provide guidance on dose reduction (as needed).

Post-Treatment Phase

Tapering Period (Weeks 21 to 23):

During the following 3 weeks the dose of SM will be gradually reduced until the subject is no longer taking the SM, so that by the end of Week 23 the subject is out of SM. Dose tapering will also be required for subjects who discontinue early during the titration period (Week 3 through Week 8) or maintenance period (Week 9 through Week 20). Subjects who discontinue early at an MTD of 25 mg/day will not undergo a dose tapering period but will return to the clinic to complete the EOS procedures (all procedures scheduled to be performed at Visit 9) within 1 week after discontinuation of SM.

End of Study (Visit 9):

[figure not shown]
All subjects who complete the study (Week 20) will return to the clinic for a final safety evaluation at the end of the Tapering Period (Visit 9). During this visit, subjects will complete the EOS procedures: clinical laboratory tests, AE assessments, vital signs, concomitant medications review, ECG, physical and neurological evaluations, eye exam, urine pregnancy test (FOCP only) and urine drug screen, headache disability, HRQoL, C-SSRS and cognitive assessments. The remaining SM and the Headache Diary device, if applicable, will be collected, and safety follow-up instructions will be provided to caregivers.

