- Collect urine sample for drug screen
- Administer C-SSRS

- Administer PedMIDAS, PedsQL 4.0
- Perform cognitive assessment
- Review and record concomitant medications
- Review Headache Diary
- Record AEs
- Collect SM and assess adherence
- Dispense 3-week supply of SM and provide instructions for dose tapering

Visit 9 (Day 162 ± 7 days) – End of Study (EOS) Visit

The following assessments will be conducted at this visit:

- Perform physical examination (excluding genitourinary system) including height and weight, and neurological examination
- Perform 12-lead ECG
- Record vital signs (pulse rate, BP, temperature, and RR)
- Collect blood samples for hematology and serum chemistry
- Collect urine sample for urinalysis and for pregnancy testing (FOCP only)
- Collect urine sample for drug screen
- Perform visual neurological exam
- Perform eye exam
- Administer C-SSRS
- Review and record concomitant medications
- Administer PedMIDAS, PedsQL 4.0 scales
- Perform cognitive assessment
- Record AEs
- Collect SM and assess adherence

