7.11 Safety Analysis

Safety analysis as described below will be conducted using the Safety Analysis Set. All safety analyses will be performed on the Safety Analysis Set.

The incidence rate of AEs will be calculated by treatment group for each System Organ Class (SOC) and Preferred Term (PT). The severity of the AEs and the relationship to

SM will be summarized by treatment group for each SOC and PT. AEs will be summarized using discrete summaries at the subject and event level by SOC and PT, and by severity and relationship separately for each treatment group. Verbatim description and MedDRA SOCs and PTs for all AEs will be contained in the subject data listings.

All AEs occurring after randomization and throughout the study period will be recorded. For subjects who receive SM, TEAEs will be collected starting after the first dose of SM (Visit 3) to the end of the study. These AEs include those that emerge during treatment or worsen in severity during treatment. These AEs will be tabulated, listed and analyzed.

The incidence of AESIs based on AE data will be summarized for each treatment group by MedDRA SOC and PT. Supporting subject listing of AESI will be presented. For AESIs, percentages of subjects experiencing visual/ocular disturbances, oligohydrosis, hyperthermia, metabolic acidosis (serum bicarbonate), hyperammonemia, nephrolithiasis, and hepatic injury will be summarized using descriptive statistics by treatment and collection time point. Clinical laboratory values will be summarized by visit and treatment group using descriptive statistics. For quantitative laboratory parameters, both actual values and change from baseline (values collected at Screening) will be summarized.

Vital signs will be summarized by visit by treatment group using descriptive statistics. Both actual values and change from baseline will be summarized.

ECG results will be summarized by visit by treatment group using descriptive statistics (for quantitative ECG parameters) and frequency tables (for qualitative ECG parameters, including the overall ECG finding).

C-SSRS outcomes will be summarized using number and percent of subjects by categories for suicidal ideation only, suicidal behavior only and suicidality (ideation and behavior combined). The summary will be presented by treatment groups.

For physical, neurological, and eye examinations, change in status from baseline to the EOS will be summarized by body system for each treatment group.

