### **9.5.     Physical, Neurological and Eye Examination**

Physical examinations will include assessments of all body systems except genitourinary as well as height and weight and a special assessment for the occurrence of decreased sweating and elevation in body temperature above normal. Neurological examination will include evaluation for impaired reflexes, balance problems, muscle weakness, paresthesia/numbness and tingling, speech difficulties, mental confusion or excessive fatigue. Eye examinations will measure visual acuity and visualize the optic disc through a fundoscopic exam. Subjects will be monitored for visual/ocular disturbances and potential signs of angle closure glaucoma during the participation in the study

Any findings during screening will be recorded as medical history and any clinically significant abnormal findings during treatment will be recorded as an AE. At the EOS physical and neurological examinations, only changes from the screening visit will be noted.

All physical, neurological and eye examination results will be listed.

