### **10. Changes from Planned Analysis**

There is no change from the planned analyses specified in the protocol.

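### The on-drug physical, neurological and eye examinations have no specified by-arm summary; the only one specified is baseline to EOS, at the end of the taper

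*Protocol*

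**What the plan says.** Protocol 7.11 deals with the three examinations in one sentence, which provides that "change in status from baseline to the EOS will be summarized by body system for each treatment group". It names no other time point for them.

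The synopsis, under Safety Analyses, is broader but less specific: "Descriptive statistics will be presented for demographics, data from the clinical laboratory test results, vital signs, weight, ECGs, physical, neurological and eye examinations". It gives neither a visit nor a table format.

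SAP 9.5 describes what each examination covers and then gives its only output: "All physical, neurological and eye examination results will be listed". SAP 10 states: "There is no change from the planned analyses specified in the protocol".

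On timing, Protocol 3.1 plans "a Dose Tapering Period of 1 to 3 weeks" after the 20-week Treatment Phase and places EOS (Visit 9) at its end. Protocol 5.1.6 schedules Visit 9 for Day 162, with a window of 7 days either side. At Visit 8 (Day 141, same window) the site is to "Dispense 3-week supply of SM and provide instructions for dose tapering", so the Visit 8 examination is the last scheduled one before the dose comes down. Under Protocol 3.4.2, early terminators have the Visit 9 procedures within a week of stopping study medication.

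**The concern.** These examinations are safety endpoints: physical and neurological in Protocol 2.6, with the eye examination added in SAP 5.3. Protocol 6.8.5 gives the on-treatment neurological evaluation a specific job, which is to look for effects of SPN-538 on the nervous system. A drug effect is best compared between arms while children are taking the drug.

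Protocol 3.2.2 says that topiramate AEs depend on dose, often pass, and may ease when the dose is cut. If examination changes behave in the same way, a change present at Visit 6, 7 or 8 could be gone by Visit 9. It would then be absent from the one by-arm examination table that the plan specifies. At stake is the descriptive safety comparison. The primary efficacy conclusion does not depend on it.

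**Working it through.** The plan gives no figure to reproduce. The check sets the examination schedule (Protocol Table 2, 5.1.1 to 5.1.6, 6.8.5 and 6.8.6) against the outputs named in the two documents.

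| Examination | Baseline | On drug | EOS | By-arm summary with a named time point |
|---|---|---|---|---|
| Physical and neurological | Visit 1 | Visits 4, 6, 7, 8 (Days 29, 85, 113, 141) | Visit 9 (Day 162) | Baseline to EOS only |
| Eye | Visit 3 | Visit 6 (Day 85) | Visit 9 | Baseline to EOS only |
| Visual neurological | Visit 1 | none | Visit 9 | Baseline to EOS only, if counted as part of the neurological examination |

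1. **On-drug examinations.** Each completer has four scheduled physical and neurological examinations and one eye examination on drug. Neither document names a by-arm table for any of them.

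2. **Distance from EOS.** Visit 8 to Visit 9 is nominally 162 − 141 = 21 days. With both windows it runs from 155 − 148 = 7 to 169 − 134 = 35 days. From the only on-drug eye examination to EOS is 162 − 85 = 77 days.

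3. **Dose at EOS.** The synopsis tapers by one 25 mg capsule a week. A child on four capsules at nominal Visit 8 takes three on Days 141–147, two on Days 148–154 and one on Days 155–161. If Visit 9 falls on Days 155–161, that child is on 25 of 100 mg; from Day 162 the child is off drug. A child starting from two or three capsules finishes sooner. EOS status is thus read at a reduced dose or after stopping. A completer held at one capsule is left aside, because no taper is described for that case.

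4. **Could baseline to EOS mean any time up to EOS?** Protocol 6.8.5 and SAP 9.5 both treat the EOS physical examination as a comparison of that visit with screening. Where the SAP wants the treatment period covered, it says so: SAP 9.2, 9.3 and 9.4 call for shift tables by visit and to the worst post-baseline value. SAP 9.7 summarizes cognitive responses by visit and arm, and SAP 9.6 counts C-SSRS responses at any point.

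5. **What other tables capture.** Protocol 6.6 defines an AE broadly enough to include any unfavourable, unintended sign. Protocol 6.6.2 requires investigators to look for AEs at each contact after the first dose, by questioning and where appropriate by examination. Protocol 6.8.5 makes clinically significant on-treatment findings AEs. SAP 9.1 tabulates TEAEs by arm, including by maximum severity. Protocol 7.11 summarizes listed AESIs, including visual disturbance, oligohydrosis and hyperthermia, by treatment and time point. SAP 9.3 summarizes weight, BMI and temperature by visit and arm.

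The remainder is on-drug examination change that is not reported as an AE.

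**The case against.** The strongest reply is that little is lost. A newly emergent balance problem, weakness, paraesthesia or speech difficulty would ordinarily meet the AE definition and enter the by-arm TEAE tables. The cognitive questionnaire (Appendix 10.5), given at Visit 3 and Visits 5 to 9, asks about tiredness, slowing, answering questions and attention, so it overlaps with part of the neurological examination. The remark about transient, dose-related effects in Protocol 3.2.2 concerns AEs, which are already tabulated by arm. All of this stands and sets the size of the point. It does not supply a by-arm table of on-drug examination status, and the AE route depends on the investigator judging a change to be reportable.

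A second reply is that the listing sentence in SAP 9.5 adds to Protocol 7.11 and does not replace it. SAP 1 says the SAP gives details beyond the protocol, and its summary of changes records that the sentence giving it precedence was deleted. This also stands. A reader might infer that the SAP has withdrawn the EOS summary, but the documents do not support that. The two sections simply fail to match, and SAP 10 does not explain why.

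The synopsis line is a by-arm commitment not limited to EOS. Because it names no visit or format and SAP 9.5 does not carry it out, it does not specify an on-drug summary.

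**Conclusion.** The point holds as a modest gap in the safety tables. The only by-arm examination summary with a stated time point is read after dose reduction or stopping, and the four physical and neurological examinations and one eye examination made on drug have none specified. The SAP section meant to implement the protocol's summary gives listings only.

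A reader might infer that neurological or ocular harm on drug would go unseen between arms. The documents do not support that, given the TEAE, AESI, cognitive and SAP 9.3 summaries. Nor would multiplying the schedule by the number of children measure the information lost: no abnormality rate is given, and most notable findings have another route into a by-arm table.

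The conclusion assumes that the table shells, which were not available, add nothing beyond the text. That examination changes short of an AE would fade with dose as AEs do is an analogy from Protocol 3.2.2; the protocol does not state it.

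**What to change.** In Protocol 7.11 and SAP 9.5, add by-arm shift tables of examination status from baseline to each on-treatment examination visit: Visits 4, 6, 7 and 8 for physical and neurological, and Visit 6 for eye. Add one further shift to the last on-drug examination. For completers that is Visit 8 (physical and neurological) and Visit 6 (eye). For early terminators it is the last earlier on-drug examination, with the number in each arm who have none.

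Keep the baseline-to-EOS table, state it in both documents, and label it post-taper. That also makes the statement in SAP 10 accurate on this point. The visual neurological examination is done only at Visits 1 and 9, so it cannot be given an on-drug summary; say so in a footnote.

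The cost is programming and a few extra descriptive tables. No visit or procedure is added, and there is no multiplicity cost because SAP 9 plans no inferential safety tests.

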8 DOCUMENTATION

8.1 Adherence to the Protocol

The Investigator agrees, when signing the protocol, to adhere to the instructions and procedures described within and to the principles of ICH GCP as well as all governing local regulations and principles for medical research.

The protocol, ICF/IAF, and appropriate related documents must be reviewed and approved by an IRB constituted and functioning in accordance with ICH E6 and any local regulations. Documentation of IRB compliance with the ICH and any local regulations regarding constitution and review conduct will be provided to the Sponsor.

A signed letter of study approval from the IRB must be sent to the Investigator with a copy to the Sponsor prior to study start and the release of SM to the site by the Sponsor or its designee. If the IRB decides to suspend or terminate the study, the Investigator will immediately send the notice of study suspension or termination by the IRB to the Sponsor.

8.2 Changes to the Protocol

Changes to the protocol will not be made without written approval from the Sponsor.

Any change to the protocol requires a written protocol amendment or administrative change that must be approved by the Sponsor before implementation. Amendments specifically affecting the safety of subjects, the scope of the investigation, or the scientific quality of the study require additional approval by the applicable IRB, and in some cases, filings to the regulatory authority. These requirements should in no way prevent any immediate action from being taken by the Investigator, or by the Sponsor, in the interest of preserving the safety of all subjects included in the study. If an immediate change to the protocol is felt by the Investigator to be necessary for safety reasons, the Medical Monitor and IRB must be notified promptly.

Changes to the protocol that are administrative in nature do not require formal protocol amendments or IRB approval, but the IRB must be kept informed of such changes. In these cases, the Sponsor will send a letter to the IRB detailing such changes.

8.3 Data Quality Assurance

This study will be organized, performed, and reported in compliance with the protocol, SOPs, working practice documents, and applicable regulations and guidelines. Site visit audits may be made periodically by the Sponsor's Quality Assurance team or qualified designee, which is an independent function from the study conduct team.

8.3.1 Data Collection

The primary source document will be the subject's medical record. If separate research records are maintained by the Investigator(s), both the medical record and the research

record will be considered the source documents for the purposes of monitoring and auditing the study.

Electronic data collection techniques will be used to collect data directly from the study sites using eCRFs. The electronic data will be stored centrally in a fully validated clinical database.

Data recorded on source documents will be transcribed into the eCRFs in accordance with the eCRF Completion Instructions that are provided to the study sites. The Investigator is responsible for ensuring that all sections of each eCRF are completed correctly, and that entries can be verified against source documents. The eCRFs will be monitored for completeness and accuracy against the source documents by the CRA(s) on a regular basis. Inconsistencies between the eCRFs and source documents will be resolved in accordance with the principles of GCP.

8.3.2 Clinical Data Management

Data from eCRFs and other external data (e.g., laboratory data) will be entered into or merged with a clinical database as specified in the data management plan. Quality control and data validation procedures will be applied to ensure the validity and accuracy of the clinical database.

